#### **7. Reporting of Adverse Events or Unanticipated Problems involving Risk to Participants or Others**

Information regarding AEs is to be obtained and documented by the surgery center anesthesia attending and/or the investigator performing the data collection and by questioning or examining the patient. All new complaints and symptoms (i.e., those not existing prior to signing of informed consent) will be recorded on the AE CRF. All AEs will be characterized in terms of their start and stop dates, start and stop times, intensity, action taken, relationship to research study, subject outcome and whether or not the AE led to an SAE.

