#### **4. Exclusion Criteria**

- A. Allergy to local anesthetics, dexamethasone, or adhesive tape
- B. Patients undergoing hamstring graft for ACL
- C. Preexisting infection at site of needle insertion
- D. Immunocompromised patients
- E. Preexisting sensory or motor deficit in operative extremity
- F. Patient on chronic opioid treatment.
- G. Patient having a revision of previous ACL reconstruction.
- H. Pregnancy and lactating women

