#### **6. Study Method**

Patients undergoing ACL reconstruction at Vanderbilt Bone and Joint Surgery Center by [name] will be identified at surgical scheduling and conveyed to anesthesia team for inclusion into study. The assigned in-room providers will be educated on the protocol and randomization process.

After written informed consent is obtained by either the patient or the designated surrogate decision maker, patients will be randomized to 2 groups: (1) continuous adductor canal nerve catheter or (2) long-acting single bolus adductor canal nerve block.

Following random selection via random envelope selection patients will receive the following procedures. Both groups will receive ultrasound guided femoral nerve block with 20cc of 2% mepivacaine <20 minutes prior to in room time.

Intraoperative patients will undergo initiation of general anesthesia under the care of the attending anesthesiologist assigned to the patient. Induction will include a propofol bolus and placement of laryngeal mask airway. Intraoperative opioid should be limited to no more than 150mcg of fentanyl. Upon completion of wound closure, appropriate dressing placement, emergence from anesthesia and removal of LMA, patients to be taken to PACU. Once adequately awake and alert, Group 1 patients will receive ultrasound guided adductor canal continuous nerve catheter using normal saline as bolus for placement, followed by initiation of 1/8% bupivacaine infusion through catheter at 8cc/h. Group 2 will receive ultrasound guided adductor canal nerve block with 10cc of 0.5% ropivacaine + 2mg dexamethasone (0.5cc), keeping total injectate at 10.5cc to spare significant proximal spread to femoral nerve. After adequate instruction including catheter education (if applicable) patients are to be discharged home.

The following data will be collected by evaluation by study investigators via phone calls:

- Subjective Numeric Rating Pain Scale score (NRPS) at discharge from PACU

- Subjective Numeric Rating Pain Scale score (NRPS) 48 hours following discharge from PACU.
- PONV score on POD 1 following discharge from PACU
- Subjective Numeric Rating Pain Scale score (NRPS) on POD 1 and 3.
- Opioid utilization based on number of pain pills (standardized dose) on POD 1, 2, and 3.
- Quadriceps strength in operative leg utilizing “Straight Leg Raise” Test, 0-5/5 scale.
- Quadriceps strength in operative leg utilizing knee extension, 0-5/5 scale.

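### Section 7 requires an AE entry only for complaints that are new since consent, so worsening of a complaint already present need not be recorded.

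*Combined protocol and SAP*

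**What the plan says.** The AE rule is in Section 7 of the combined protocol and SAP. Information is to be gathered "by the surgery center anesthesia attending and/or the investigator performing the data collection and by questioning or examining the patient". The recording sentence follows: "All new complaints and symptoms (i.e., those not existing prior to signing of informed consent) will be recorded on the AE CRF". Each event is then described by its timing and by "intensity, action taken, relationship to research study, subject outcome and whether or not the AE led to an SAE".

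Section 6 (Study Method) places consent before everything that could cause harm in the trial: "After written informed consent is obtained by either the patient or the designated surrogate decision maker, patients will be randomized to 2 groups". The femoral block, surgery, and catheter or single injection come later.

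Section 4 (Exclusion Criteria) removes patients with "Preexisting sensory or motor deficit in operative extremity". It also removes those on long-term opioids ("Patient on chronic opioid treatment"), but it does not exclude pain or swelling in the knee.

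Section 6 also collects some symptoms as study data, apart from the AE form. These include pain, for example "Subjective Numeric Rating Pain Scale score (NRPS) 48 hours following discharge from PACU", and nausea and vomiting ("PONV score on POD 1 following discharge from PACU").

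**The concern.** An AE rule normally has two limbs: events that are new, and existing conditions that get worse. Section 7 has only the first. Its bracketed definition makes absence before consent the test, so a complaint that was mild at consent and severe after the procedure does not meet it.

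Patients awaiting ligament reconstruction may well have a symptomatic knee, and those aged 14 and over may have other conditions. For them, a recorder who follows the sentence has no instruction to enter a deterioration. The AE form is the only general safety record that the plan describes. An omission there is recovered only if another study item happens to capture the same symptom.

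**Working it through.** No figure in the plan bears on this point, so the check sets the sections side by side. The inputs are the recording sentence in Section 7, the exclusions in Section 4, and the data list and 6-week visit in Section 6.

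**Step 1. Does any other sentence cover worsening?** Section 7 has three sentences: who gathers the information and how, what is recorded, and how each event is described. Only the second sets a criterion. Section 8 (Statistical Considerations) adds nothing on AEs. Worsening is therefore not addressed anywhere.

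**Step 2. Which complaints can fall into the gap?** A complaint must be able to exist at consent, and its worsening must not be collected elsewhere.

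| Complaint | Can it exist at consent? | AE entry required if it worsens? | Collected elsewhere? |
|---|---|---|---|
| Numbness in operative leg | No (exclusion E) | Not applicable: any occurrence is new and recordable | No sensory item |
| Weakness in operative leg | No (exclusion E) | Not applicable: any occurrence is new and recordable | Strength tests, including at 6 weeks |
| Knee pain | Yes | No | Yes: PACU discharge, POD 1, 48 hours, POD 3, 6 weeks |
| Knee swelling | Yes | No | No |
| Nausea or vomiting | Yes | No | Partly: POD 1 score |
| Other medical condition not excluded in Section 4 | Yes | No | No |

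The real gap is the swelling row and the last row. Pain falls outside the AE rule when it was present at consent, but its severity is still measured.

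**Step 3. How large is it?** Let *p* be the share of the 100 patients with an uncollected complaint at consent. The number in whom a worsening could go unrecorded is at most 100 × *p*, and the number of missed events depends also on how often such complaints worsen. The documents give neither quantity and do not bound *p*, so I give no count.

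**Step 4. Can the test be applied?** Both the present rule and an extended one need to know what existed before consent. The data list in Section 6 begins at PACU discharge and names no baseline symptom record. Preoperative clinical notes may supply one, but the plan does not say so.

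**The case against.** The strongest reply is that the sentence sets a minimum. It says that all new complaints are recorded, and it does not say that nothing else may be. This stands. A reader might infer that worsening can never be an AE here, but the text leaves it unaddressed rather than barred. What remains is that entry is left to the recorder's discretion. Two kinds of recorder are named and no blinding is described, so that discretion need not be used consistently.

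A reader might also infer that signs found on examination fall outside the rule because the sentence names only complaints and symptoms. The preceding sentence lists examination as a source of AE information, so that inference is not supported. Naming signs in the revised sentence merely removes the doubt.

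A third tempting inference is that ordinary postoperative pain and block numbness will flood the AE form, put nearly every patient at one or more events, and make AE counts uninterpretable. The documents do not support this:

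- Knee pain already present at consent is not new under the rule, so surgical pain is not an AE in every patient.
- Timing, intensity and relationship are recorded for each event, so brief expected numbness can be told apart from prolonged or severe events.
- The same rule applies to both arms, and consent precedes randomisation.
- AEs are not a listed outcome, and no comparison of them between arms is planned.
- No figure in the documents supports a proportion near 100%.

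**Conclusion.** The concern holds in limited form. Section 7 requires entries for new complaints only, and nothing else in the plan requires an entry when an existing complaint worsens. The safety record can therefore be incomplete, chiefly for knee swelling and for medical conditions outside the operative leg's nerve function.

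Two features of the plan narrow the gap: the exclusion of preexisting sensory or motor deficit in the operative leg, and the separate collection of pain severity. The conclusion rests on reading the recording sentence as it stands and on some patients having a complaint at consent, a share that the documents do not give. It does not touch the primary outcome or the power statement, and it does not show bias between the arms. It is a gap in wording that is worth closing because closing it is nearly free.

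**What to change.** Replace the recording sentence in Section 7 with:

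> All untoward signs, symptoms or events that are new, or that worsen in severity or frequency compared with before consent, will be recorded on the AE CRF.

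Do not add an exemption for expected numbness or weakness. Section 6 has no sensory item, so exempted numbness would be recorded nowhere. If only weakness persisting to the 6-week visit counted, weakness that resolved earlier could be lost from the AE record. Also avoid any recording trigger that can occur in one arm only. Early catheter removal, for example, is possible only in Group 1 and would make AE ascertainment unequal by design.

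Keep recording these effects with the timing, intensity and relationship already required. If AEs are summarised, tabulate expected block effects and surgical pain separately from other events. A short note of complaints present at consent would make the comparison workable, and the current rule already depends on that information.

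The cost is a few words in Section 7, a matching CRF instruction and slightly more AE recording. The design and sample size do not change.

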#### **8. Statistical Considerations**

Power calculations based on using 2 groups to detect a 2-point reduction in pain on numerical pain scale yields an 88% power. All individual data (including any relevant derived variables) will be stored in a password protected electronic database (REDCAP).

#### **9. Privacy/Confidentiality Issues**

All reasonable efforts will be made to keep a patient's protected health information (PHI) private and confidential. There will be limited access to medical records and de-identification of all records. Federal privacy guidelines will be followed when using or sharing any protected health information.

